8.1.3 Enrollment

In advance of Visit 0, the site team will review all notes from Screening visits, medical assessments, IR assessments, notes, discussions, medical records, and measures against eligibility criteria. If the participant is eligible, medication tapering and concomitant medications dose adjustments will be discussed, if applicable. The site physician will consult the prescribing physician to initiate medication tapering for participants. For all details on concomitant medications, tapering, allowed, and prohibited medications refer to [Section 12.0 Concomitant Medications](#).

At study onset at each site, if a potential participant is eligible, the study team will contact the Medical Monitor and send a summary of the medical history for approval to enroll the potential participant. After the Medical Monitor establishes confidence in the enrollment procedures at each site, the Medical Monitor will inform the site that for future participants they need only contact the Medical Monitor if they have questions about further participants' eligibility. If a participant is approved by the sponsor, the participant will be notified of enrollment at Visit 0 in-person, via telemedicine, or by telephone. Medical history and medication information will be reviewed for completeness. A medication tapering plan will be discussed with the participant, if applicable. If agreeable, the participant will be enrolled in the study. Once enrolled, AE collection requirements begin (refer to [Section 11.0 Safety](#)). Visit 0 should take place 2 to 14 days after Independent Rater Screening is completed. Visit 0 and Visit 1 may take place on the same day.

8.2 Preparatory Period with Enrollment Confirmation

Participants will undergo three Preparatory Sessions (Visits 1, 2, and 4) lasting approximately 90 minutes with the therapy team prior to the first Experimental Session. The Preparatory Period will be initiated within 12 days of Visit 0 and last 1 to 11 weeks, depending on duration of medication tapering. There must be at least 48 hours between Preparatory Sessions. The minimum time to complete the Preparatory Period is 5 days. The Preparatory Period will also include the Baseline CAPS-5 assessment (Visit 3), which will be assessed by a blinded IR. Adherence criteria for Preparatory Sessions should be followed per the Treatment Manual. In these visits the therapy team will work with the participant to prepare for MDMA-assisted psychotherapy, begin building therapeutic alliance, and promote a safe set and setting for confronting trauma-related memories, emotions, and thoughts.

8.2.1 Preparatory Sessions 1 and 2

Preparatory Sessions during the Preparatory Period will focus on psychoeducation about PTSD, building safety for the therapeutic relationship, developing the therapeutic alliance, obtaining the background for the trauma, and preparing the participant for the first Experimental Session. Telephone calls may be scheduled between visits if indicated for tapering, safety, or any further questions about medical history.

The Preparatory Sessions will be scheduled as follows:

- Preparatory Session 1 (Visit 1) will occur 0 to 12 days after Visit 0. The visit timing should take in to account appropriate times for monitoring medication tapering.

- Preparatory Session 2 (Visit 2) will occur 2 to 21 days after Visit 1. The visit timing should take into account appropriate times for monitoring medication tapering.
- If tapering is ongoing at Preparatory Session 2 (Visit 2), the site team will schedule a telephone phone call within 7 days of completion of tapering and stabilization to confirm that the participant is eligible for the Baseline CAPS-5 assessment. If tapering is complete or not needed, the site team will confirm eligibility and schedule Baseline CAPS-5 T1 (Visit 3) and Preparatory Session 3 (Visit 4) as soon as possible.

At each 90-minute psychoeducation and psychotherapy Preparatory Session, the therapy team will:

- Record the therapy session.
- Inquire about any possible changes in health to ensure the participant continues to meet all eligibility requirements. Record AEs as described in [Section 11.0 Safety](#).
- Inquire about concomitant medication use and adherence.
- Confirm that medication tapering is ongoing or complete, as appropriate.
- Discuss goals and expectations for the Experimental Session, following standard procedures and techniques described in the Treatment Manual [106].

If a participant would like a companion present during or after the Experimental Session, a meeting between the therapy team and that individual will be scheduled prior to the first Experimental Session. There must be mutual agreement between the participant and therapy team concerning the presence of the companion.

During one of the Preparatory Sessions, if possible, the therapy team will introduce the participant to the attendant who will remain with the participant during each overnight stay after each MDMA-assisted psychotherapy session. The attendant will be an individual with previous training in managing psychological distress. The site will make all attempts to have the same attendant for each Experimental Session for a given participant, but it is not guaranteed.

At any time during the Preparatory Period, if a potential participant is deemed to be ineligible, the site team will classify them as a Pre-randomization Early Termination, notify the potential participant that they are unfortunately not eligible for the study, and not schedule additional assessments. The site team will not randomize participants classified as Pre-randomization Early Terminations.

8.2.2 Baseline: CAPS-5 by Independent Rater

At Visit 3, an IR will measure the Baseline CAPS-5 (referred to as Baseline CAPS-5 T1) via telemedicine as soon as possible after medication tapering, stabilization, and two Preparatory Sessions are complete. This visit may be recorded to video to establish inter-rater reliability. The scores will be sent as soon as possible to the site staff. A CAPS-5 Total Severity Score of at least 35 is required to meet Enrollment Confirmation criteria. The IR will also administer the DSP-I and SDS.

Due to possibilities of negative side effects of withdrawal from psychiatric medications, the Baseline CAPS-5 should be scheduled as close to the end of tapering as clinically appropriate so that participants who do not meet eligibility criteria can resume their previously prescribed medications as quickly as required for symptom management and participants who do meet criteria can be enrolled and treated as quickly as possible.

8.2.3 Baseline: Preparatory Session 3 & Enrollment Confirmation

Prior to Visit 4, the site team will review the results of the IR visit to ensure that the CAPS-5 Total Severity Score is at least 35. Visit 4 should be scheduled 3 to 6 days after the Baseline CAPS-5 assessment and 1 to 4 days before Experimental Session 1 (Visit 5).

At Visit 4, the site team will confirm eligibility by reassessing specified eligibility criteria and ensuring that the participant continues to agree to all lifestyle modifications. If the participant continues to be eligible for the study, enrollment will be confirmed (after approval from the Medical Monitor for the initial participants until confidence is established). If any requirements are not met before or during Visit 4, the participant will be considered a Pre-randomization Early Termination.

For eligible participants at Visit 4, qualified site staff will:

- Perform urine pregnancy test for participants who are of childbearing potential.
- Perform urine drug test.
- Administer Since Last Visit C-SSRS to determine suicidal risk.
- Actively support participant in the completion of Baseline self-reported measures. Completion of measures does not need to be recorded.
 - ACE
 - BDI-II
 - CPGS
 - EQ-5D-5L
 - IASC
 - IPF
 - SCS
 - TAS-20
 - SRNU
 - EAT-26
 - HPQSF
 - UFEC
- Complete the third 90-minute Preparatory Session (as described in [Section 8.2.1 Preparatory Sessions 1 and 2](#)) with the purpose of confirming all enrollment is met and completing final preparation for the first Experimental Session.
- Remind the participants of lifestyle modifications, including fasting and refraining from using psychoactive or non-approved medications, pertinent prior to the Experimental Session per [Section 4.3 Lifestyle Modifications](#).
- Schedule Visit 5.

8.3 Treatment Period

During the Treatment Period, which occurs over a duration of 9 to 15 weeks (Visits 5 to 18), participants will complete three treatments. Each treatment consists of an Experimental Session, followed the morning after by an Integrative Session, phone follow-ups over the next week, a second Integrative Session within 2 weeks, and a third Integrative Session within 3 to 5 weeks. The Experimental Sessions will be scheduled 3 to 5 weeks apart. The CAPS-5 will be assessed at two time points during the Treatment Period: CAPS-5 T2 after Integrative Session 1.2 (Visit 7) and CAPS-5 T3 after Integrative Session 2.2 (Visit 12). The Primary Outcome CAPS-5 (T4) will be assessed after the last Experimental Session during the Follow-up Period.

8.3.1 Experimental Sessions

There will be three blinded Experimental Sessions (Visits 5, 10, 15). Procedures for MDMA-assisted psychotherapy will remain the same across all sessions and all procedures regardless of dose received. Experimental Sessions must be at least 8 hours long, measured from 30 minutes prior to IMP administration.

Experimental Sessions will be scheduled as follows:

- Experimental Session 1 (Visit 5) will occur within 4 to 7 days after the Baseline CAPS-5 (Visit 3) assessment; 1 to 4 days after Preparatory Session 3 and Enrollment Confirmation (Visit 4). Experimental Session 1 (Visit 5) must occur within 7 days of the Baseline CAPS-T1 (Visit 3) and after Preparatory Session 3 and Enrollment Confirmation (Visit 4). If the Baseline CAPS-5 assessment is completed outside of the allowed window, the investigator should consult the CRA and Medical Monitor to determine if the assessment should be repeated. The first Experimental Session will include 80 mg of IMP followed by a supplemental half-dose 1.5 to 2 hours after the initial dose unless contraindicated.
- Experimental Session 2 (Visit 10) will occur 21 to 35 days after Experimental Session 1 (Visit 5) and at least 1 day after Integrative Session 1.3. A dose of 80 or 120 mg MDMA or placebo will be administered. A supplemental half-dose will be administered 1.5 to 2 hours after the initial dose unless contraindicated.
- Experimental Session 3 (Visit 15) will occur 21 to 35 days after the second Experimental Session (Visit 10) and after Integrative Session 2.3. A dose of 80 or 120 mg MDMA or placebo will be administered. A supplemental half-dose will be administered 1.5 to 2 hours after the initial dose unless contraindicated.

Table 7: Schedule of Procedures for Experimental Sessions

Approximate Time	Procedure or Action
9:30	Urine drug screen and pregnancy test, concomitant medication information collected, participant acclimated to environment, C-SSRS
9:55	Baseline BP (Blood Pressure), body temperature, pulse
10:00	IMP Administration , Begin video recording
11:30	BP, body temperature pulse Supplemental Dose Administration , unless contraindicated
17:30	C-SSRS, BP, body temperature, pulse

Pre-IMP administration

- 24 to 48 hours prior to the first Experimental Session, the participant will be randomized using a web-based randomization program.
- 24 to 48 hours prior to each Experimental Session, the site team will obtain the container assignment.
- On the day of the Experimental Session, the participant will arrive approximately 30 to 60 minutes prior to IMP administration.
- The site team will ensure the participant has not used caffeine or nicotine 2 hours prior and has fasted for 10 hours prior to IMP administration and complied with all other requirements per [Section 4.3 Lifestyle Modifications](#).
- The site team will inquire about any possible changes in health to ensure the participant continues to meet all eligibility requirements and record AEs as described in [Section 11.0 Safety](#).

- The site team will instruct the participant that they will not be able to use caffeine or nicotine at least 6 hours after the IMP administration.
- The site team will complete urine drug screen, pregnancy test, and concomitant medication review.
 - A positive drug screen will be reviewed by the site physician and may be cause for delaying IMP administration to a later time, rescheduling the session to a later date, or withdrawing the participant from the study, based on Medical Monitor review.
 - A positive pregnancy screen is cause for withdrawal from the protocol.
- The therapy team will administer Since Last Visit C-SSRS.
- The therapy team will review procedures for the Experimental Session with the participant and discuss the participant's goals, intentions, and concerns and some of the commonly experienced effects of MDMA. The choice of whether to keep the dose the same or change it from the first Experimental Session will be made by the therapy team in consultation with the site physician based on observed response, tolerability to the previously administered dose, and discussion with the participant.
- If the participant continues to be eligible, the session will proceed.
- Baseline blood pressure, body temperature, and pulse will be measured just prior to administration of the initial dose.

During the Experimental Session

- After video recording has begun, at approximately 10:00 in the morning, a qualified staff member will administer the initial dose of IMP with an electrolyte-containing fluid. The participant will sit or recline on comfortable furnishings. Eyeshades and a program of music will be provided for the participant if they wish to use them. Whenever they wish, participants may speak to the therapy team, who will provide guidance and support, as needed.
- After the first hour, if the participant has not spoken spontaneously, the therapy team will check in with them about the nature of the experience. For the rest of the experience, as appropriate, the therapy team will support and encourage the participant in emotional processing and resolution of whatever psychological material is emerging, as described in the Treatment Manual.
- Electrolyte-containing fluids will be provided throughout the session but not to exceed three liters overall.
- Blood pressure, body temperature, and pulse will be measured approximately 1.5 to 2 hours after the initial dose, before the supplemental dose is administered.
- If the participant prefers not to have the supplemental dose, the therapy team will document the reason.
- The site physician will be contacted with a brief description of how the session is progressing and the recent vital signs. The site physician will approve or deny the administration of the supplemental dose. If an AE requiring medical attention has occurred between the initial and supplemental dose, the site physician will determine whether the supplemental dose is contraindicated. If medical attention is needed, the site physician will provide further instruction or consult the Medical Monitor.
- A supplemental half-dose will be administered with a glass of electrolyte-containing fluid approximately 1.5 to 2 hours after the initial dose, unless contraindicated.
- Food will be provided during the latter part of the session.
- If there is an approved companion, that person may arrive as agreed upon but will wait in the waiting room until a member of the therapy team brings them to the session room. Alternatively, the companion may arrive after the session has ended.

End of Experimental Session

- The therapy team will administer Since Last Visit C-SSRS.
- The therapy team will record AEs and concomitant medications.
- The session may be ended if all medical and psychiatric parameters are acceptable, elevations in vital signs have resolved to pre-IMP levels, the participant is alert, ambulatory, and emotionally stable, and the night attendant has arrived.
- The therapy team or site physician shall remain available to participants via 24-hour cellular phone for integration, as needed.

Overnight Stay (See [Appendix A](#) for sub-study with exceptions)

- Participants will remain overnight in an appropriately furnished room at or near the study site until after the Integrative Session the morning after each Experimental Session. The stay will be in an appropriately furnished room at the study site. With prior approval of the therapy team, a companion may accompany the participant during the overnight stay.
- An attendant will check in periodically on the participant during the overnight stay, even if a companion is present. The attendant will monitor participant condition and will help participants relax during the overnight stay. The attendant will be an individual with some previous training in managing psychological distress and will be supportive but not intrusive. If there is an emergency or the participant needs additional support, the attendant can contact the therapy team.
- The participant and a companion (if applicable) will receive information that will allow them to contact the therapy team during the overnight stay in the case of an emergency or to request for additional support.
- Participants will be encouraged to use much of the time during their overnight stay for rest and as a period of reflection and integration in a quiet atmosphere.
- The participant will be driven home after the integration session by either a driver arranged by the participant, by site personnel, or taxi.

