5.3.4 Early Termination from the Study

Participants who are removed from the study after they are randomized and receive IMP but do not complete the study may fall into one of these categories: Post-randomization Early Termination or Dropout. If the participant has received IMP in at least one Experimental Session and completed one CAPS-5 assessment beyond Baseline, they will be considered evaluable. All participants who receive IMP in at least one Experimental Session will be included in all safety analyses.

Participants can withdraw from treatment or withdraw consent at any time for any reason without judgment. The site team can withdraw a participant if, in their clinical judgment, it is in the best interest of the participant or if the participant cannot comply with elements of the protocol that are critical for safety or for the scientific integrity of the study. If the site team makes the decision to terminate the participant from treatment or the study, they will explain the reason for withdrawal and document in the participant’s source records and Electronic Case Report Form (eCRF). If a participant develops any Exclusion Criteria that, in the opinion of the Medical Monitor or Site, affects the safety of the participant, including psychiatric diagnosis, medical diagnosis, pregnancy, or requiring use of prohibited medications, the participant will discontinue treatment in Experimental Sessions but remain in the study for the associated Integrative Sessions. Participants whose Experimental Sessions are delayed by the COVID-19 pandemic may start any of these medications during the delay, as clinically indicated. When study visits resume, they will be given the option to resume Experimental Sessions after tapering off of these medications per [Section 12.1 Tapering Instructions](#). Any time a participant terminates from the study early, the site team will attempt to obtain information about AE outcomes if appropriate, as determined by the site physician and Medical Monitor. The site team will provide the participant with an Exit Plan as described in [Section 8.4.3.2 Exit Plan](#).

Data will be collected from participants who terminate early as follows:

- **Post-randomization Early Termination:** Participants who discontinue study treatment but continue to participate in Independent Rater primary and secondary outcome assessments. Data collection by IRs will continue on the same schedule as planned through Study Termination visit procedures.

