- **Dropout:** If a participant decides to withdraw consent completely, they will terminate without further follow-up. If the participant agrees, they will complete a final CAPS-5 assessment. These participants are defined as dropouts who withdraw consent due to any reason after receiving at least one dose of IMP and no longer participate in the study (i.e., no further contact with investigators or site staff). Data collected on study participants up to the time of withdrawal of consent will remain in the trial database in order to maintain scientific validity. Removal of data from the database would undermine the scientific and ethical integrity of the research.

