8.4.2 Final Independent Rater Assessment

Participants will have a final CAPS-5 assessment at the completion of the follow-up period (Visit 19). A blinded IR from the IR Pool will conduct the assessments via telemedicine. These assessments may be recorded to establish inter-rater reliability. The results will not be sent to or seen by site staff but instead will be sent to a blinded IR Coordinator to enter the data which will also be blinded to the sponsor. Participants will be instructed to withhold their opinion on treatment group assignment from IRs. Although there are allowable windows for all visits throughout the protocol, the Primary Outcome CAPS-5 T4 assessment is targeted to be completed 18 weeks (± 3 weeks) (105 to 147 days) after the Baseline CAPS-5 assessment (Visit 3) and 8 weeks (± 2 weeks) (42 to 70 days) after Experimental Session 3 (Visit 15). If there are significant delays in the timing of Experimental Session 2 (Visit 10) and/or Experimental Session 3 (Visit 15), the visit should be scheduled 8 weeks (± 2 weeks) (42 to 70 days) after Experimental Session 3 (Visit 15). Participants who have withdrawn from treatment will also complete a final CAPS-5 assessment immediately upon withdrawal. The IR will also administer the DSP-I and SDS.

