8.4.3 Study Termination

Study Termination (Visit 20) will take place 1 to 9 days after the final CAPS-5 assessment (Visit 19). Participants who have withdrawn from treatment but have continued for follow-up will also complete this assessment immediately upon withdrawal.

The site team will:

- Inquire about any possible changes in health. Assess the participant's mental health and the status of any previously recorded AEs. Record AEs as described in [Section 11.0 Safety](#).
- Inquire about concomitant medication use and adherence.
- Administer Since Last Visit C-SSRS.
- Measure weight (used to calculate BMI).
- Measure blood pressure.
- Provide and discuss a study exit plan.
- Ask them to enroll into the LTFU extension study with a visit at 12 months after the last Experimental Session. Review contact information and Informed Consent procedures for LTFU.
- Review potential timeline until study unblinding and how they will be informed of their treatment group at that time.
- Actively support participant in completion of Study Termination self-reported measures. Completion of the measures does not need to be recorded.
 - LEC-5
 - BDI-II
 - CPGS
 - EQ-5D-5L
 - IASC
 - IPF
 - SCS
 - TAS-20
 - AUDIT
 - DUDIT
 - SRNU
 - EAT-26
 - HPQSF

After all Study Termination measures and assessments are completed, the participant is considered terminated from the study. The participant can resume normal everyday life. The study team will provide an Exit Plan, which may include a referral for additional medical or therapeutic care, as described in [Section 8.4.3.2 Exit Plan](#). Eligible participants will be asked to participate in the LTFU extension study, described in [Section 8.4.3.1 Extension Studies](#).

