11.3.3 Follow-up Requirements

Details of all pregnancies in study participants will be collected after Enrollment (Visit 0) and collected through 10 days after the last Experimental Session. Pregnancies should be reported to the sponsor via telephone or email within 24 hours of site staff awareness.

In the event of a pregnancy, the participant will discontinue Experimental Sessions but may continue with non-drug Integrative Sessions, the next CAPS-5 assessment, and Study Termination procedures. At a minimum, prior to withdrawal from the study, efforts should be made to assess the final CAPS-5 immediately and complete Study Termination procedures. The participant will be emergency unblinded if the participant wishes as described in [Section 9.4 Blinding](#), after the final CAPS-5 assessment.

The investigator will collect follow-up information on the participant and neonate and forward to the sponsor until the outcome of the pregnancy, which will be reported on an optional Pregnancy eCRF. Any termination, elective or spontaneous, will be reported. Abnormal pregnancy outcomes, such as spontaneous abortion, fetal death, stillbirth, congenital abnormalities, or ectopic pregnancy, will be reported as SAEs.

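### Protocol 8.4.3 closes out at once the treatment discontinuers whom 5.3.4 and SAP 8.2 keep on the planned schedule; 8.3.1 is also out of step with 5.3.4 on pregnancy

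*Protocol*

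**What the plan says.** **After stopping treatment.** Protocol 5.3.4 defines Post-randomization Early Terminations as "Participants who discontinue study treatment but continue to participate in Independent Rater primary and secondary outcome assessments", and then states: "Data collection by IRs will continue on the same schedule as planned through Study Termination visit procedures". SAP 8.2 repeats that rule and gives limiting missing data as the reason. Two other sections agree with it. Outside COVID-19 delays, Protocol 12.3 takes participants who use an antidepressant after Visit 5 off treatment and continues them in follow-up. Protocol 9.4 has the sponsor monitor for complete data, including from treatment discontinuers.

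Protocol 8.4.2 reads differently: "Participants who have withdrawn from treatment will also complete a final CAPS-5 assessment immediately upon withdrawal". So does Protocol 8.4.3, on the Study Termination visit: "Participants who have withdrawn from treatment but have continued for follow-up will also complete this assessment immediately upon withdrawal". Section 8.4.3 adds that a participant counts as terminated once that visit's measures are done.

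Participants who withdraw consent have their own rule in 5.3.4. They have no further follow-up, except that "If the participant agrees, they will complete a final CAPS-5 assessment".

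**Pregnancy.** Protocol 8.3.1, in the checks before dosing: "A positive pregnancy screen is cause for withdrawal from the protocol". Protocol 5.3.4 lists pregnancy among the events after which "the participant will discontinue treatment in Experimental Sessions but remain in the study for the associated Integrative Sessions". Protocol 11.3.3 says "the participant will discontinue Experimental Sessions but may continue with non-drug Integrative Sessions, the next CAPS-5 assessment, and Study Termination procedures". For someone who is withdrawing, 11.3.3 asks for efforts to obtain an immediate final CAPS-5 and Study Termination procedures first.

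**The concern.** No section says which rule prevails. A site that follows 8.4.3 as worded would close out a participant who was willing to stay, and rater, AE and C-SSRS collection would end weeks early. That is a wrong rule, not a missing detail, because 8.4.3 names the very group that 5.3.4 keeps on schedule.

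Two things are at stake. The first is the de facto analysis in SAP 8.7.2, which is meant to use CAPS-5 data collected after treatment discontinuation. The SAP argues that this analysis has no missing data because everyone's data collection continues, and 8.4.3 undercuts that argument. The second is routine safety follow-up of dosed participants with severe PTSD: scheduled AE collection runs to Visit 20 (Protocol 11.1), and the C-SSRS is scheduled at that visit (Protocol Table 6).

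The pregnancy wording raises the same problem for fewer people. Staff facing a positive test on a dosing day will be reading 8.3.1, and its bullet does not point to 5.3.4 or 11.3.3.

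**Working it through.** **Step 1: the rules side by side.**

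| Group | Protocol 5.3.4 and SAP 8.2 | Protocol 8.4.2 and 8.4.3 |
|---|---|---|
| Stopped treatment, still in follow-up | Rater visits as planned, through Study Termination | Final CAPS-5 now (8.4.2, all who withdrew from treatment); Study Termination now (8.4.3) |
| Withdrew consent | One final CAPS-5 if willing, then no follow-up | Not named |

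The immediate visits would fit the second row. As worded, they apply to the first.

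**Step 2: how early the last rating would come.** The plan gives no figure to reproduce. Inputs:

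- Visit 3 to Visit 5: 4 to 7 days (Protocol 8.3.1)
- Visit 5 to Visit 10: 21 to 35 days (Protocol 8.3.1 and Table 1; Table 5 shows 21 to 25, and I use the wider window)
- Visit 10 to Visit 15: 21 to 35 days (Protocol 8.3.1)
- Visit 3 to Visit 19: 105 to 147 days (Protocol 8.4.2)

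Section 8.4.2 also times Visit 19 from Experimental Session 3. I leave that anchor out, because a participant who stops at or before the Visit 15 date never has that session.

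Days after Visit 3:

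- Visit 10: 4 + 21 = 25 to 7 + 35 = 42
- Visit 15: 25 + 21 = 46 to 42 + 35 = 77

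Gap from an immediate final CAPS-5 to the planned Visit 19 (earliest Visit 19 minus latest stop, to latest Visit 19 minus earliest stop):

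- Stop at the Visit 10 date: 105 − 42 = 63 to 147 − 25 = 122 days
- Stop at the Visit 15 date: 105 − 77 = 28 to 147 − 46 = 101 days

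A rating at the Visit 10 date would therefore describe days 25 to 42 after Baseline, not about week 18.

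These gaps belong to the immediate-rating route. If 8.3.1 were followed with no closing rating, the last CAPS-5 would be Visit 8 or Visit 13. Each of those falls on or before an Integrative Session held 1 to 7 days ahead of the dosing day, so the gap would be longer.

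**Step 3: how many participants.** SAP 8.7.2 expects no more than 5% to discontinue treatment after the first session and its CAPS-5: 0.05 × 100 = 5. This is an expectation and not a ceiling; Protocol 2.2.4 reports Phase 2 dropout of 8 of 107, or 7.5%. The documents give no pregnancy rate, so I put no number on that subgroup. A positive screen at Visit 5 precedes any IMP and puts nobody in the mITT or Safety set, so the pregnancy point concerns Visits 10 and 15.

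**The case against.** The strongest reply is that the plan's intent is clear: 5.3.4, SAP 8.2, 12.3 and 9.4 all point to continued follow-up, and 8.4.3 is the outlier. The word *also* in 8.4.2 can mean an extra rating on top of Visit 19, and nothing there cancels Visit 19. That reading of 8.4.2 is fair, although calling the rating *final* works against it. It does not rescue 8.4.3, where completing the visit ends participation for people it describes as continuing.

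On pregnancy, the reply has more force. A reader might infer that 8.3.1 flatly contradicts 11.3.3, but 11.3.3 is permissive. It offers continuation only to the next CAPS-5 and Study Termination procedures, and it also provides for withdrawal with an immediate final CAPS-5. So 8.3.1 can be read as choosing the second route. The conflict that remains is with 5.3.4, and it too is qualified. That clause depends on the Medical Monitor's or site's opinion that safety is affected. It keeps the participant for the associated Integrative Sessions, which for a dosing-day positive at Visit 10 or 15 are already complete for the preceding treatment. Even so, remaining in the study and being withdrawn from the protocol are different instructions.

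A reader might also infer that dosed participants, or pregnant ones, are left without safety follow-up. The documents do not support that. Existing AEs are monitored to resolution, with a clinical decision on further follow-up at termination (11.1). AE outcomes are sought after early termination where appropriate (5.3.4). The pregnancy is followed to its outcome (11.3.3).

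**Conclusion.** The main claim holds: 8.4.3 is wrong as written, and 8.4.2 is at best ambiguous, when set against 5.3.4 and SAP 8.2. The pregnancy wording in 8.3.1 is a real but secondary conflict with 5.3.4.

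It would be tempting to conclude that the primary result is at risk. It is not, because the de jure analysis in SAP 8.7.1 leaves out CAPS-5 data collected after treatment discontinuation. The exposure is limited to an analysis that the SAP calls exploratory and supportive, and to scheduled AE and C-SSRS collection. It concerns about 5 of 100 participants if the SAP's 5% expectation holds, with an unknown and probably small number of pregnancies among them. For someone stopping at the Visit 10 or Visit 15 date, the last rating would come 63 to 122 or 28 to 101 days ahead of the planned Visit 19. Those ranges assume the stated visit windows are kept. The point should be corrected, but it does not threaten the trial's main conclusion.

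**What to change.** **Protocol 8.4.2 and 8.4.3.** Limit the immediate final CAPS-5 and the immediate Study Termination visit to participants who are leaving the study, in line with the Dropout rule in 5.3.4. State that participants who stop treatment but continue follow-up complete Visits 19 and 20 on the 5.3.4 schedule.

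**Protocol 8.3.1.** Replace the pregnancy bullet with: *If the pregnancy screen is positive, Experimental Sessions stop. Participants who have received IMP are followed per Sections 5.3.4 and 11.3.3 unless they withdraw consent. Participants who are positive at Visit 5, before any IMP, are withdrawn.*

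**Protocol 11.3.3.** Leave the unblinding rule as it is, after the final CAPS-5. Unblinding earlier and then continuing to rate would put unblinded Visit 19 ratings into the de facto analysis, for which the SAP has no handling rule.

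The cost is wording in three protocol sections. No SAP change is needed, and no visits are added beyond those 5.3.4 already requires. One consequence should be accepted openly: a pregnant participant who stays to Visit 19 and wants to know their assignment learns it after that rating, unless an emergency calls for unblinding under Protocol 9.4.
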